12.4.2 Case Report Forms

Copies of pertinent records in connection with the study, including all source documents, will be made available to the Sponsor or its designee on request with due precaution towards protecting the privacy of the patient.

Data will be entered by the site into the eCRFs in the EDC system. Unless explicitly directed, blank data fields are not acceptable. Any erroneous entries made in the eCRFs must be corrected. Changes made to the data after initial entry into the eCRF will be captured via an electronic audit trail, and include the reason for change. Incomplete entries or entries needing additional explanation will be highlighted or queried to the Investigator for clarification.

12.4.3 Record Retention

The Investigator is responsible for oversight and maintenance of the study records and patient source documents. These records must be readily available for audit or inspection.

The Investigator must retain study records for at least 2 years after completion of the clinical study. However, these documents should be retained for a longer period, if required by other applicable requirements (e.g., applicable local regulatory requirement) or by an agreement with

the Sponsor or its designee. The Investigator will contact the Sponsor or its designee prior to any record destruction.

Patient records or other source data must be kept for the maximum period of time mandated by the hospital, institution, or private practice, but not less than 15 years.

If off-site archiving is used, all records must be retrieved and made available for review at the time of an audit or regulatory authority inspection.

12.4.4 Monitoring

A representative of the Sponsor or its designee will remotely interface with and may visit the Investigator periodically for the purpose of monitoring the progress of this study in accordance with the protocol, GCP, and local regulations. A monitor, auditor, IRB and or/other regulatory authority, such as the The United States Food and Drug Administration (FDA), would have access to study-related medical documents for the purposes of the study. Non-compliance with the protocol, GCP, and local regulations will be documented and corrective actions implemented, as necessary. It is the responsibility of the Investigator to be present or available for consultation during remote or on-site monitoring visits. In order to complete remote or on-site monitoring visits, all data pertaining to a patient's participation in this clinical investigation must be made available to the monitor.

At any time prior to, during, or after completion of the clinical study, an audit may be performed by the Sponsor or its designee or a representative of a national regulatory agency may choose to inspect a study site; this includes FDA. The FDA may inspect all records related to the study. Investigators must notify the Sponsor or its designee upon notification of inspection by a representative of a national regulatory agency. A Sponsor or designee representative will be available to assist in the preparation for study site inspections. All pertinent study data must be made available for verification, audit, or inspection purposes.

12.4.5 Study or Site Termination

If the Sponsor or its designee, the Investigator, or regulatory authorities discover any conditions during the study that indicate that the study or study site should be terminated, this action may be taken after appropriate consultation between the Sponsor or its designee and the Investigator. The Sponsor or its designee has the right to terminate the participation of either an individual site or the study at any time, for any reason which may include the following:

- The incidence and severity of AEs in this or other studies indicates a potential health hazard to patients.

- Patient enrollment is unsatisfactory.
- Data recording is inaccurate or incomplete.
- Investigator(s) do(es) not adhere to the protocol or applicable regulatory guidelines in conducting this study.
- Submission of knowingly false information from the study site to the Sponsor or its designee, or regulatory authorities.

In the event that the study is terminated early, the Sponsor or its designee will provide specific guidance to investigational sites regarding the end-of-study procedures.

12.4.6 Investigational Product Control

Not applicable.

12.4.7 Insurance

The Sponsor will maintain a liability insurance policy covering all clinical studies under its sponsorship, and that policy will comply with local laws and requirements. The Sponsor or its designee will provide a certificate of insurance to any IRB/IEC or regional Health Authority that may require such a document. Note that this Sponsor insurance coverage does not relieve the Investigator, the Institution, and their collaborators from each maintaining their own liability insurance policy for their clinical research activity.

12.4.8 Disclosure of Data

All details related to the disclosure and publication of study data will be addressed in the Investigator's study contract.

12.4.9 Clinical Study Report

The Sponsor or the Sponsor's designee is responsible for preparing a clinical study report. The final report is signed by the Sponsor. Study results will be provided to the Investigators.

Concomitant Medications/Therapies ²	X	
Blood draw for Plasma Cholestanol testing and Genetic testing ³	X	
Urine collection for Bile Alcohol testing (if urine sample is provided) ⁴	X	
Serious Adverse Events related to procedures	X	
Genetic Testing for CTX ⁵		X
Photographic Documentation of Cataracts ⁶		X
Follow-Up Notification of Results	X ⁷	X ⁸
Study Discontinuation	X ⁷	X ⁸

¹ History of or current manifestations of signs and symptoms commonly associated with CTX

² Concomitant medications and therapies during the week prior to enrollment will be collected.

³ Blood draw may be collected in conjunction with other scheduled treatments during medical care that is separate from the clinical study

⁴ Urine sample (if provided) may be collected in conjunction with other scheduled treatments during medical care that is separate from the clinical study

⁵ Will be completed if patient plasma cholestanol level is $\geq 0.4\text{mg/dL}$ ($4\mu\text{g/mL}$) or urine bile alcohol is positive (if urine sample is provided)

⁶ If available, collected for patients who have been diagnosed with CTX.

⁷ For those participants with *normal results* for plasma cholestanol $< 0.4\text{ mg/dL}$ ($4\mu\text{g/mL}$) and urine bile alcohol is negative (if urine sample is provided), participation ends after tests results have been communicated to the patient and study discontinuation page is completed.

⁸ For those participants who *require genetic testing*, participation ends after reporting of test results to the patient, and study discontinuation page is completed.

List of Abbreviations

AE	Adverse Event
CDCA	Chenodeoxycholic Acid
CRFs	Case Report Forms
CSR	Clinical Study Report
CTX	Cerebrotendinous Xanthomatosis
DMC	Data Monitoring Committee
ICH	International Conference on Harmonization
MedDRA	Medical Dictionary for Regulatory Activities
PT	Preferred Term
SAE	Serious Adverse Event
SAP	Statistical Analysis Plan
SOC	System Organ Class
TOC	Table of Content
WHO	World Health Organization

1 INTRODUCTION

This document describes the statistical methods and data presentations to be used to assess the prevalence of cerebrotendinous xanthomatosis (CTX) in patient populations diagnosed with early-onset idiopathic bilateral cataracts. Background information is provided for the overall study design and objectives. The reader is referred to the study protocol, 018CTXX15001 dated 13 December 2016, and case report forms (CRFs) for details of study conduct and data collection.

The proposed analysis methods and approaches in this statistical analysis plan (SAP) should be viewed as flexible. If the data suggest and warrant it, deviations from the SAP will be considered. However, any deviations from the SAP must be substantiated by sound and convincing statistical rationale and documented in the clinical study report (CSR).

2 OBJECTIVES AND ENDPOINTS

2.1 Objectives

2.1.1 Primary Objective

To calculate the prevalence of CTX in a patient population diagnosed between the ages of 2 and 21 years old (inclusive) with early-onset idiopathic bilateral cataracts.

2.1.2 Secondary Objective

To assess other manifestations of CTX within patients presenting with idiopathic bilateral cataracts.

2.2 Endpoints

- Proportion of patients with positive CTX test based on
 - Elevated plasma cholestanol level ≥ 0.4 mg/dL (4 μ g/mL) or
 - Positive urine bile alcohol results among those with urine sample
- Proportion of patients with confirmed CTX based on genetic testing for mutations associated with CTX among those with non-missing plasma cholestanol or urine bile alcohol results
- Proportion of patients with confirmed CTX based on genetic testing for mutations associated with CTX among those with elevated plasma cholestanol levels or positive urine bile alcohol results
- Plasma cholestanol, plasma cholesterol, and urine bile alcohol levels

- Incidence of serious adverse events (SAEs) associated with study procedures (i.e. a blood draw)

3 INVESTIGATIONAL PLAN

3.1 Study Design

This is an observational, multicenter study to determine the prevalence of CTX in patient populations diagnosed or treated for early-onset idiopathic bilateral cataracts, identified through a chart review of patients who were seen at each study site prior to that site's initiation or by entering care at the site while the site is participating in the trial.

Approximately 500 patients are to be enrolled in this study.

Participation will be limited to persons between the ages of 2 to 21 years old (inclusive) at the time of diagnosis with idiopathic bilateral cataracts. For specific inclusion/exclusion criteria, please refer to the study protocol, 018CTXX15001.

Participation in the study is limited to one or more study visit(s) for collection of study data, including a blood draw and urine sample (if provided). These procedures will typically be completed in a single visit, but additional visits are permitted if a blood sample is not obtained or a replacement blood sample is required for any reason. The length of a patient's participation will be from the time the informed consent form is signed until results of the CTX testing have been obtained and reported to the patient. Study participation for patients who have normal test results for plasma cholestanol and urine bile alcohol (if urine sample is provided) will be complete after reporting of these test results to the patient. Study participation for patients who require genetic testing will be complete after reporting of these test results to the patient. For a complete schedule of events, please refer to [9.1](#).

3.2 Treatments

No treatments will be administered during this observational study.

4 GENERAL CONSIDERATIONS FOR DATA ANALYSIS

As an observational study, there are no statistical hypotheses regarding treatment effects. Rather, displays and comparisons of patient data will primarily utilize descriptive statistics, as noted below.

Unless otherwise specified, continuous variables will be summarized by presenting the number of non-missing observations, mean, standard deviation, median, minimum, and maximum. Categorical variables will be summarized by presenting the number of patients and percentage for each category.

Minimum and maximum values will be presented to the precision of the original value. Means and medians will be rounded to one decimal place greater than the precision of the

original value. Standard deviation and 95% confidence intervals will be rounded to two decimal places greater than the precision of the original value. Percentages for summarizing categorical data will be rounded to one decimal place.

All summary tables will be based on pooled data across centers. By-patient listings, including data collected at all visits, will be sorted by patient number, study visit, and then by date/time of the records.

Analyses will be performed using SAS® version 9.4.

4.1 Analysis Sets

All patients who signed the informed consent will be included in the Screened Set. All patients who signed the informed consent and whose eligibility was established will be included in the Enrolled Set. All screened patients who undergo invasive study procedures (i.e. a blood draw) will be included in the Safety Set.

4.2 Assessment Windows

The study schedule of events appears in [9.1](#). Study patients are expected to attend a single clinic visit, during which all study procedures will be performed. No analysis windows are planned regarding data collected in the study.

4.3 Handling of Multiple Lab Observations

If multiple lab records exist at a collection time point, the repeated record will be used for data summary.

4.4 Handling of Missing or Invalid Data

Missing data will remain missing. Missing data including partial dates will not be imputed. Data points that appear to be invalid will be queried for correction or confirmation by the clinical site.

4.5 Interim Analysis

No interim analysis is planned. There is no Data Monitoring Committee (DMC) for this study.

4.6 Determination of Sample Size

Approximately 500 patients will be enrolled in the study. Because this is an observational, non-interventional study, no power calculation has been performed. The study size is considered to be appropriate to investigate the prevalence of CTX among patients diagnosed or treated for early-onset idiopathic bilateral cataracts.

5 STUDY PATIENTS

5.1 Analysis Sets

The number and percentage of patients in each analysis set will be summarized. The data will also be listed.

5.2 Subject Eligibility

Subject eligibility for the study (inclusion and exclusion criteria failures) will be listed for the Screened Set.

5.3 Disposition of Patients

Patient disposition will be presented for the Screened Set. The number and percentage of patients who complete or discontinue the study, as well as the discontinuation reasons, will be provided. In addition, the number of patients who have plasma samples, urine samples, or genetic tests will be summarized.

A patient listing for study disposition will be provided for the Screened Set.

5.4 Demographics and Baseline Characteristics

Demographics and baseline characteristics (age, sex, race, and ethnicity) will be analyzed using the Enrolled Set. Summary statistics (n, mean, median, standard deviation, minimum, and maximum) will be reported for continuous variables, whereas counts and percentages will be reported for categorical variables. A listing of demographics will be provided.

5.5 Medical History

A targeted medical history is collected for all patients enrolled in the study. It includes any history of, or current manifestation of, signs and symptoms commonly associated with CTX. Medical history terms will be coded using the Medical Dictionary for Regulatory Activities (MedDRA) version 24.0. The number and percentage of patients with each medical condition will be summarized by System Organ Class (SOC) and Preferred Term (PT) for the Enrolled Set.

All medical history data (including family history) will be listed.

5.6 Prior and Concomitant Medications

Concomitant medications and therapies the patient has taken in the week prior to enrollment will be recorded during the study visit(s). Concomitant medications will be coded using WHODrug Global B3 released in March 2021. Each verbatim term will be classified by anatomical main group (ATC level 1), therapeutic subgroup (ATC level 2), pharmacological

subgroup (ATC level 3), chemical subgroup (ATC level 4), and chemical substance (ATC level 5).

The number and percentage of patients using concomitant medications will be summarized by ATC level 2 and preferred term using the Enrolled Set.

All prior and concomitant medication data will also be listed.

5.7 CTX Testing Analyses

Results of CTX testing (plasma cholestanol, plasma cholesterol, urine bile alcohol, and genetic testing) will be summarized using the Enrolled Set when data are available.

Summary statistics (n, mean, median, standard deviation, minimum, and maximum) will be reported for continuous variables. Frequency counts and percentages will be reported for categorical variables. A listing of CTX testing data will also be provided.

Additionally, the prevalence of CTX will be examined on the basis of the following percentages, reported together with 95% confidence intervals:

1. Patients with a plasma cholestanol level ≥ 0.4 mg/dL (4 μ g/mL).
2. Patients with a positive test for urine bile alcohol.
3. Patients with a plasma cholestanol level ≥ 0.4 mg/dL (4 μ g/mL) or a positive test for urine bile alcohol.
4. Patients with a positive genetic test for CTX.
5. Patients with a positive genetic test for CTX among those with elevated plasma cholestanol level or positive urine bile alcohol result.

For criteria 1 and 2, denominator of the percentage will be based on the number of patients with non-missing results. For criteria 3 and 4, denominator of the percentage will be based on the number of patients with either plasma cholestanol or urine bile alcohol results reported. Two-sided 95% confidence intervals will be calculated using the exact Clopper-Pearson method.

SAS® sample code for the Clopper-Pearson method:

```
data clop_ci;
set lb;
p=round ((x/n), .001);
if p=0 then CI_LOW=0;
if p=1 then CI_HIGH=1;
if p ne 0 then CI_LOW=round((1-betainv(.975, (n-x+1), x)), .00001);
if p ne 1 then CI_HIGH=round((1-betainv(.025, (n-x), x+1)), .00001);
run;
```

Table 1 lists the mapped genetic testing results that will be used for summary.

Table 1: Genetic Testing Results

Mapped Genetic Testing Result	Reported Genetic Testing Result
Positive	Positive
	Likely positive
Negative	Inconclusive
	Negative
	No mutations identified
	No biochemical evidence of CTX
	No mutations were identified
	No mutations found

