
Exclusion Criteria:
 
A patient who meets any of the following criteria will be excluded from this study.
 
 1. The patient has a diagnosis of cataracts with known etiology other than CTX. 2. The patient has a diagnosis of CTX. 3. The patient has cataracts caused by cataractogenic treatments. 4. The patient has taken or is currently taking cholic acid or chenodeoxycholic acid. 5. The patient has received an investigational product in an interventional clinical trial in the past 30 days. 6. The patient and/or their parent/legal guardian, in the opinion of the Investigator, is unable to adhere to the requirements of the study.

DOSE/ROUTE/REGIMEN (TEST ARTICLE): Not applicable – this is an observational study

REFERENCE TREATMENT: Not applicable

CRITERIA FOR EVALUATION: The plasma cholestanol levels and/or urine bile alcohol results (if urine sample is provided) will be used to determine whether genetic testing is indicated. Genetic testing, if indicated, will be used to determine the prevalence of CTX.

STATISTICAL METHODS:
 
Power and Sample Size: Approximately 500 patients will be enrolled in the study. Because this is an observational study, no power calculation has been performed. The study size is considered to be appropriate to investigate the prevalence of CTX among patients diagnosed or treated for early-onset idiopathic bilateral cataracts.
 
Analysis Sets: All study patients for whom results of cholestanol or urine bile alcohol testing (if urine sample is provided) are available will be included in the analysis dataset. All study patients who undergo study procedures (i.e., a blood draw) will be included in the safety dataset.
 
Demographics and Baseline Characteristics: Descriptive statistics will be used.
 
Efficacy: There are no efficacy endpoints in this descriptive, observational study.

NAME OF COMPANY

Retrophin, Inc.
[name]
[name]
USA

NAME OF FINISHED PRODUCT

Not Applicable

NAME OF ACTIVE INGREDIENT

Not Applicable

Safety:

Serious Adverse Events associated with study procedures (i.e., a blood draw) will be listed.

CTX Testing:

Plasma cholestanol levels, urine bile alcohol results (if urine sample is provided), and results of genetic testing for CTX will be summarized using descriptive statistics.

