Suspicion of CTX is typically based on clinical symptoms, most often including chronic diarrhea with infantile onset, bilateral cataracts in children, and the appearance of xanthomas on the Achilles tendons, extensor tendons of the elbows and hands or patellar tendons, often by the third decade of life.[8] Biochemical abnormalities that indicate likely CTX are elevated bile and plasma cholestanol levels, increased ratio of serum cholestanol/cholesterol, increased urinary excretion of bile alcohol glucuronides and diminished biliary concentrations of chenodeoxycholic acid (CDCA).[9, 10] In clinical practice, elevated plasma cholestanol and urine bile alcohol are used as tests for probable CTX, with the diagnosis confirmed by a finding of mutation in the *CY 27A1* gene on chromosome 2q35-qter.[8, 11]

Treatment of cerebrotendinous xanthomatosis

CDCA has long been considered to be the standard of care for the condition. CDCA treatment is effective in preventing adverse clinical manifestations of the disease from occurring or progressing if the treatment is administered early enough.[12] Though the extent of published evidence is limited, available clinical studies and case reports suggest that the ability of CDCA treatment to reverse existing adverse clinical manifestations is mixed, with some manifestations being at least partially reversed and others stabilizing. Initiation of CDCA treatment as early as possible is universally recommended by experts, before irreversible damage has occurred.[13] There are also published reports of cholic acid being used instead of CDCA.[14, 15, 27] Recently, cholic acid has been approved for the treatment of bile acid synthesis disorders, including CTX [27].

Other treatments that have been reported to be combined with CDCA treatment in clinical practice are: Vitamin D, Vitamin E, anti-seizure medications, L-dopa-carbidopa, anti-psychotic medications, anxiolytics, anti-depressants and statins.[16-23] In a small number of reported

cases, statins were given without CDCA.[22, 24] Apheresis treatment has also reported in a small number of cases, in combination with CDCA or alone.[7, 25, 26]

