4 STUDY OBJECTIVES

The primary objective of this study is to calculate the prevalence of CTX in a patient population diagnosed between the ages of 2 and 21 years old (inclusive) with early-onset idiopathic bilateral cataracts.

The secondary objective of this study is to assess other manifestations of CTX within patients presenting with idiopathic bilateral cataracts.

5 INVESTIGATIONAL PLAN**5.1 Endpoints****5.1.1 Efficacy Endpoints**

This study has no treatments and no efficacy endpoints.

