8.5 CTX Testing (if necessary)

Blood and urine (if urine sample is provided) will be collected during the study for testing of the plasma cholestanol and urine bile alcohol levels. The following is applicable:

- If the plasma cholestanol level is < 0.4 mg/dL (4 μ g/mL) and urine bile alcohol is negative (if urine sample is provided) then no further testing is required.
- If the plasma cholestanol level is ≥ 0.4 mg/dL (4 μ g/mL) or urine bile alcohol is positive (if urine sample is provided), this will prompt genetic testing.
 - If a patient is diagnosed with CTX, photographic documentation of cataracts, if available, will be obtained from the patient's clinical records for the study data files.
- The Investigator may be notified if the plasma total cholesterol level (fasting or nonfasting) is > 190 mg/dL. These results are provided for medically informative purposes only.

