8 TABLE OF CONTENT (TOC) FOR OUTPUTS

Table 2: TOC for Tables and Listings

Output Type	Output Name	Analysis Set
Table	Analysis Sets	Screened Set
Table	Patient Disposition	Screened Set
Table	Demographics and Baseline Characteristics	Enrolled Set
Table	CTX Medical History	Enrolled Set
Table	Concomitant Medications	Enrolled Set
Table	CTX Testing Results	Enrolled Set
Table	Prevalence of CTX	Enrolled Set
Table	Overall Summary of Procedure-related or possibly related AEs	Safety Set
Table	Procedure-related or possibly related AEs by SOC and PT	Safety Set
Listing	Analysis Sets	Screened Set
Listing	Subject Eligibility	Screened Set
Listing	Patient Disposition	Screened Set
Listing	Demographics and Baseline Characteristics	Enrolled Set
Listing	CTX Medical History	Enrolled Set
Listing	Family History	Enrolled Set
Listing	Concomitant Medications	Enrolled Set
Listing	CTX Testing Results	Enrolled Set

Listing	Procedure-related or possibly related AEs	Safety Set
---------	---	------------

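### Does the SAP leave open which of its five percentages is the prevalence of CTX?

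*SAP*

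**What the plan says.** The study has one primary question. Protocol 4 states: "The primary objective of this study is to calculate the prevalence of CTX in a patient population", and SAP 2.1.1 repeats it. The Protocol synopsis (Criteria for Evaluation) gives the biomarkers the job of deciding who is genetically tested, and then says: "Genetic testing, if indicated, will be used to determine the prevalence of CTX". The diagnosis part of Protocol 3 agrees: "elevated plasma cholestanol and urine bile alcohol are used as tests for probable CTX, with the diagnosis confirmed by a finding of mutation". Under Protocol 8.5, the rule for a patient whose biochemical screen is negative is "then no further testing is required".

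SAP 2.2 lists its endpoints without ranking them. It does separate a positive CTX test (biomarkers) from confirmed disease, and its second bullet is the proportion with "confirmed CTX based on genetic testing for mutations associated with CTX among those with non-missing plasma cholestanol or urine bile alcohol results".

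SAP 5.7 then says that "the prevalence of CTX will be examined on the basis of the following percentages, reported together with 95% confidence intervals" and lists five items. It sets denominators for items 1 to 4, builds the denominator of item 5 into that item's wording, and specifies two-sided Clopper-Pearson intervals. SAP 8, Table 2, lists an output titled "Prevalence of CTX" on the Enrolled Set, and a separate table of CTX testing results. No table shells are shown.

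**The concern.** A prevalence study should say in advance which number is its prevalence. SAP 5.7 introduces all five percentages as bases for prevalence, yet items 1 to 3 count patients who trigger genetic testing, and item 5 is conditional on having triggered it. Neither SAP 2.2 nor Protocol 4 ties a particular endpoint to the primary objective. SAP 1 also describes its methods as flexible.

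If the study report led with a biomarker rate or with item 5, the stated prevalence could be several times the genetically confirmed figure. Item 4 also carries an assumption that the SAP does not spell out: screen-negative patients, who have no genetic test, count as non-cases.

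**Working it through.** **Step 1. Classify the five percentages.** Numerators and denominators are from SAP 5.7, and the matching endpoints from SAP 2.2.

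| Item | Numerator | Denominator | What it measures | SAP 2.2 |
|---|---|---|---|---|
| 1 | cholestanol at or above 0.4 mg/dL | patients with a cholestanol result | screen-positive rate | bullet 1 |
| 2 | urine bile alcohol positive | patients with a urine result | screen-positive rate | bullet 1 |
| 3 | either positive | patients with either result | screen-positive rate | bullet 1 |
| 4 | genetic test positive | patients with either result | confirmed CTX among all tested | bullet 2 |
| 5 | genetic test positive | screen-positives | confirmed CTX among screen-positives | bullet 3 |

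**Step 2. Apply the documents' own rules.** The synopsis requires a genetic numerator, which removes items 1 to 3. The primary objective concerns the cataract population and not its screen-positive part, which removes item 5. Only item 4 remains.

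**Step 3. Check the unstated assumption in item 4.** Genetic testing follows only a positive screen (Protocol 8.5; footnote 5 of the schedule in SAP 9.1). The denominator of item 4 is everyone with a biomarker result. Screen-negatives are therefore in the denominator and cannot enter the numerator, so their treatment as non-cases can be deduced from the SAP alone. Table 1 in SAP 5.7 states openly that an inconclusive genetic result is mapped to negative. Screen-positives with no genetic result stay in the denominator as it is defined.

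**Step 4. Size of a misreading.** The documents give about 500 patients, no power calculation and no expected counts, so there is no planned figure to reproduce. Let N be the number tested, s the number screen-positive and g the number genetically positive. All values of s and g below are assumptions, and N = 500 assumes that every patient has a biomarker result.

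- Item 3 = s/N, item 4 = g/N, item 5 = g/s.
- If every genetic positive is also screen-positive, item 4 = item 3 × item 5. Then item 3/item 4 = s/g and item 5/item 4 = N/s.
- Clopper-Pearson limits for x out of n: the 0.025 quantile of Beta(x, n−x+1) and the 0.975 quantile of Beta(x+1, n−x).

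| s, g | Item 3 (95% CI) | Item 4 (95% CI) | Item 5 (95% CI) | s/g | N/s |
|---|---|---|---|---|---|
| 50, 3 | 10.0% (7.51–12.97) | 0.60% (0.12–1.74) | 6.0% (1.25–16.55) | 16.7 | 10 |
| 25, 2 | 5.0% (3.26–7.29) | 0.40% (0.05–1.44) | 8.0% (1.0–26.0) | 12.5 | 20 |
| 10, 10 | 2.0% (0.96–3.65) | 2.0% (0.96–3.65) | 100% (69.2–100) | 1 | 50 |

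The identity checks in the first row: 0.10 × 0.06 = 0.006. The ratios depend on the counts assumed. For s from 25 to 75 and g from 1 to 8, s/g runs from 25/8 = 3.1 to 75/1 = 75, and N/s from 500/75 = 6.7 to 500/25 = 20. For s from 10 to 50 and g from 1 to 10, s/g runs from 10/10 = 1 to 50/1 = 50, and N/s from 500/50 = 10 to 500/10 = 50.

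**Step 5. Effect of adding a label.** With g = 3, item 4 is 3/500 = 0.60% (0.12–1.74) whether or not the SAP calls it primary. The other four rows are equally unaffected.

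**The case for a change.** The best argument for a change is that a primary estimate should be stated and not inferred. The lead-in of SAP 5.7 is looser than the synopsis, because it gives rates of probable disease the same standing as confirmed disease. A descriptive study with one primary objective can still name one number, and doing so would cost a sentence.

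Part of this stands. The label is absent, the lead-in is loose, and the rows differ several-fold under most of the assumed counts. A sentence naming item 4 would be tidy and harmless.

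The rest does not carry through. The flexibility clause in SAP 1 requires any departure to have a statistical rationale and to be recorded in the study report, so it does not permit an unexplained switch of headline figure. The output list gives only a title and an analysis set; that all five rows sit under the prevalence title is a fair inference from SAP 5.7, not something the table states. The large ratios measure how wrong a misreading would be, not how likely it is, and they rest on counts the documents do not supply. Relabelling also has pitfalls: calling item 5 a positive predictive value would be strictly right only if every screen-positive patient had a conclusive genetic result.

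**Conclusion.** No change to the plan is needed. The wording gap is real, but the synopsis rule, the primary objective and the second endpoint of SAP 2.2 all lead to item 4, which is already planned with a defined denominator and an exact interval. All five percentages are to be reported under their own criteria, so nothing is concealed. The study has no hypothesis test, interim analysis or success criterion that could turn on the choice of row. The numerical effect of adding a label is zero.

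This conclusion assumes that the analysts read the SAP with the protocol, as SAP 1 directs, and that the study report keeps each percentage with its stated criterion. The several-fold differences between rows are illustrations on assumed counts and predict no error in the reported result.
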